9.7.1.7.3 PHARMACODYNAMIC, PHARMACOGENOMIC, AND OTHER BIOMARKER ANALYSES

The analysis of the biomarker endpoints defined as below will be performed to compare elenbecestat (E2609) versus placebo using the appropriate prespecified statistical methods including MMRM model, ANCOVA, or non-parametric methods if the data is not normally distributed, etc. These analyses will be conducted without adjustment for multiplicity or sequential testing. For each endpoint, the treatment effect for elenbecestat (E2609) 50 mg per day versus placebo will be tested at a significance level of 2-sided alpha = 0.05. (revised per Amendment 05)

- Change from baseline in amyloid PET SUVR composite at 24 months for brain amyloid levels
- Change from baseline in tau PET signal at 24 months (revised per Amendment 05)
- Change from baseline in CSF biomarkers t-tau and p-tau at 24 months
- Change from baseline in CSF amyloid biomarkers $A\beta(1-42)$, and $A\beta(1-x)$ at 24 months (revised per Amendment 04)

- Change from baseline in total hippocampal volume at 12 and 24 months using vMRI
- Change from baseline in the preservation of connectivity on fMRI from predefined anatomical regions connectivity maps (eg, precuneus, inferior frontal sulcus)

The relationship between exposure (in CSF, plasma) of elenbecestat (E2609) with potential biomarkers of Alzheimer's disease as deemed appropriate will be evaluated using appropriate statistical model with the continuous changes in biomarker at 24 months as response variables and exposure variables (in CSF, plasma) of elenbecestat (E2609) as independent variables.

9.7.1.8 Safety Analyses

Evaluations of safety will be performed on the Safety Analysis Set. The incidence of AEs, out-of-normal-range laboratory safety test variables, abnormal ECG findings, and out-of-range vital signs, suicidality, results of the sleep questionnaire, along with change from baseline in laboratory safety test variables, ECGs, and vital sign measurements will be summarized by treatment group. (revised per Amendment 01)

9.7.1.8.1 EXTENT OF EXPOSURE

The Duration of exposure to study drug will be summarized as cumulative extent of exposure in categories with 3-month increment. The cumulative number and percent of subjects in each applicable exposure category will be presented by treatment group. Duration of exposure will be summarized using descriptive statistics as well as by 3-month duration categories using counts. The number and percent of subjects within each duration category will be presented by treatment group. Overall exposure (number of subject-months) is defined as summation over all subjects' exposure durations and will be summarized by treatment group.

9.7.1.8.2 ADVERSE EVENTS

The AE verbatim descriptions (investigator terms from the eCRF) will be classified into standardized medical terminology using the Medical Dictionary for Regulatory Activities (MedDRA). AEs will be coded to the MedDRA (Version 19.0 or higher) lower level term closest to the verbatim term. The linked MedDRA PT and primary system organ class (SOC) are also captured in the database.

A TEAE is defined as:

- An AE that emerges on or after start of study treatment, having been absent at pretreatment (Baseline) or
- Reemerges on or after start of study treatment, having been present at pretreatment (Baseline) but stopped before treatment, or
- Worsens in severity on or after start of study treatment relative to the pretreatment state, when the AE is continuous. (revised per Amendment 04)

Only those AEs that are treatment-emergent will be included in summary tables. All AEs, treatment-emergent or otherwise, will be presented in subject data listings.

The TEAEs will be summarized by treatment group on the Safety Analysis Set. The incidence of TEAEs will be reported as the number (percentage) of subjects with TEAEs by SOC and PT. A subject will be counted only once within an SOC and PT, even if the subject experienced more than 1 TEAE within a specific SOC and PT. The number (percentage) of subjects with TEAEs will also be summarized by maximum severity (mild, moderate, or severe). The number (percentage) of subjects with TEAEs will also be summarized by relationship to study drug (Yes [related] and No [not related]).

The number (percentage) of subjects with treatment-related TEAEs will be summarized by SOC and PT. Treatment-related TEAEs include those events considered by the investigator to be related to study drug. The number (percentage) of subjects with treatment-related TEAEs will also be summarized by maximum severity (mild, moderate, or severe).

AEs will be summarized by the following subgroups: region, , prior treatment with AChEIs or memantine (no or yes), and clinical subpopulation (MCI due to AD or the early stages of AD). (revised per Amendment 01)

The number (percentage) of subjects with TEAEs leading to death will be summarized by MedDRA SOC and PT for each treatment group. A subject data listing of all AEs leading to death will be provided. The number (percentage) of subjects with treatment-emergent SAEs will be summarized by MedDRA SOC and PT for each treatment group. A subject data listing of all SAEs will be provided. The number (percentage) of subjects with TEAEs leading to discontinuation from study drug will be summarized by MedDRA SOC and PT for each treatment group. A subject data listing of all AEs leading to discontinuation from study drug will be provided.

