9.7.2 Determination of Sample Size

The sample size for this study is estimated based on comparison of elenbecestat (E2609) versus placebo with respect to the primary efficacy endpoint, the change from baseline CDR-SB at 24 months. Based on available ADNI data [amyloid positive, MMSE equal or greater than 24, late MCI (global CDR=0.5) populations from ADNI, ADNI 2 and ADNI GO] the mean and the standard deviation of the change from baseline in the CDR-SB at 24 months in the placebo group are assumed to be 1.75 and 2.05, respectively. Therefore, assuming a 25% reduction in the mean change from baseline CDR-SB at 24 months for the elenbecestat

(E2609) 50 mg per day dose group compared to placebo with a common standard deviation of 2.05 and an estimated 30% dropout rate in this study, a total sample size of 1330 subjects, 665 subjects in each treatment group, will be required to detect the treatment difference between elenbecestat (E2609) 50 mg per day and placebo using a 2-sample t-test with 90% power at a significance level of 2-sided alpha =0.05.

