9.3.3 Removal of Subjects from Therapy or Assessment

The investigator may withdraw the subject from the study at any time for safety or administrative reasons. The subject may stop study drug or withdraw from the study at any time for any reason.

Absolute lymphocyte count from the hematology and differential panel will be monitored during the study. ALC will be derived from the CBC with differential representing the normal lymphocytes (with atypical lymphocytes removed and presented as a separate count if they are present) and calculated by the white blood cell count \times percentage of lymphocytes. (revised per Amendment 02) Should a subject develop a Grade 2 or greater lymphocytopenia (less than $800/\text{mm}^3$), the absolute lymphocyte count test should be repeated as soon as possible with the repeat blood sample drawn no later than 5 calendar days from the date of the original test result. (revised per Amendment 04) If confirmed, study drug administration should be interrupted for a minimum period of 2 weeks and for a maximum period of 4 weeks. Restart of study drug may take place only when absolute lymphocyte count returns to greater than LLN. Absolute lymphocyte count will be measured 4 weeks after restart of study drug. Subsequent measurements of absolute lymphocyte counts will follow the schedule of assessments (Table 4) and any results showing a Grade 2 or greater lymphocytopenia (less than $800/\text{mm}^3$) should be handled as above. If a 2nd occurrence of Grade 2 or greater lymphocytopenia (less than $800/\text{mm}^3$), that is confirmed on repeat testing, occurs within 6 months, then the subject should be discontinued permanently from the study drug. (revised per Amendment 01)

Subjects who develop moderate or severe hepatic impairment (eg, Child-Pugh Class B or C) during the study must discontinue study drug. (revised per Amendments 02 and 03) Moderate or severe hepatic impairment are defined as any 2 of the following criteria: INR ≥ 1.7 ; bilirubin $\geq 1.5 \times \text{ULN}$; albumin $< \text{LLN}$; ascites or hepatic encephalopathy. Please note that a single significant abnormality could meet criteria for moderate impairment. (revised per Amendment 03)

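### Adverse events are summarised only as crude percentages; if exposure turns out shorter on active, those percentages can understate its risk, so exposure-adjusted rates should stand beside them

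*Protocol*

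**What the plan says.** Section 9.7.1.8.2 (Adverse Events) states the measure outright: "The incidence of TEAEs will be reported as the number (percentage) of subjects with TEAEs by SOC and PT", with each subject counted once per SOC and PT. For serious events it says: "The number (percentage) of subjects with treatment-emergent SAEs will be summarized by MedDRA SOC and PT for each treatment group". Severity, relatedness, deaths and events leading to discontinuation of study drug follow the same pattern. No event rate per unit of time and no time-to-event summary of adverse events is mentioned.

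Section 9.7.1.8.1 (Extent of Exposure) does calculate time on drug: "Overall exposure (number of subject-months) is defined as summation over all subjects' exposure durations and will be summarized by treatment group". It does not link that figure to the event counts.

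Section 9.7.2 assumes "an estimated 30% dropout rate in this study", one overall figure with no split by arm.

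Section 9.3.3 lists events that end study drug. For a second confirmed Grade 2 or greater lymphocytopenia within 6 months, "then the subject should be discontinued permanently from the study drug". Hepatic impairment of moderate or worse degree, seizures, suspected drug rash, and severe infection or moderate to severe herpes not resolved within 4 weeks also lead to permanent stopping. Section 7.1 reports herpes relapse, viral respiratory infection and drug rash in the multiple-dose study, and some reduction in CD4 counts at 50 to 100 mg. The trial dose is 50 mg.

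**The concern.** A percentage of treated subjects with an event depends on the hazard and on how long subjects are observed. If the arms are observed for equal time, the second factor cancels in a comparison. If one arm stops earlier, it does not.

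The protocol gives a reason to foresee unequal time. The stopping events in section 9.3.3 overlap with events already reported for this drug, so more early stops on active are plausible. Observation is tied to exposure as well: the last follow-up visit is 12 weeks after the last dose (section 9.1.2.2), and serious events are collected up to 12 weeks after the last dose (section 9.5.4.1). Subjects who stop early are then asked back only at 12 and 24 months, or at 24 months alone, while those who continue are seen about every 3 months from month 3 (Table 4).

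Safety is a secondary objective, and section 7 describes the trial as intended to be pivotal for registration. The planned tables are how safety would be read, and they give no adjusted figure for any SOC or PT if exposure differs.

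**Working it through.** **The plan's own figure.** From section 9.7.2: placebo mean change 1.75, reduction 25%, so the difference is 0.4375; SD 2.05; 90% power; two-sided 0.05.

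n per arm = 2 × (1.960 + 1.282)² × 2.05² / 0.4375² = 462 (rounded up); 462 / (1 − 0.30) = 660, against 665 stated. The figure reproduces within 1%. With 665 × 0.70 = 465.5 completers per arm, power is 90.2%. The 30% is therefore an inflation factor for the whole trial and says nothing about each arm.

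**Model for the crude percentage.** These are assumptions: constant event hazard λ, independent exponential dropout with hazard μ, 24 months, events counted only while on drug.

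- λ = −ln(1 − R) / 24, where R is the true 24-month risk
- μ = −ln(1 − d) / 24, where d is the dropout proportion
- crude percentage = λ / (λ + μ) × [1 − exp(−24(λ + μ))]
- mean exposure = (1 − exp(−24μ)) / μ

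For R = 20%, λ = 0.00930 per month. At d = 25%, μ = 0.01199, so the crude percentage is 0.00930 / 0.02128 × (1 − 0.80 × 0.75) = 17.5%. At d = 35%, μ = 0.01795, giving 0.00930 / 0.02725 × (1 − 0.80 × 0.65) = 16.4%. The ratio is 0.94.

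The dropout splits below are assumptions, chosen to average the stated 30%. The last column uses a hazard ratio of 1.25, for which the true 24-month risk ratio is 1.22.

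| Dropout, placebo / active | Mean exposure, months | Crude %, equal hazards | Ratio, equal hazards | Ratio shown when HR = 1.25 |
|---|---|---|---|---|
| 30% / 30% | 20.2 / 20.2 | 16.9 / 16.9 | 1.00 | 1.22 |
| 27% / 33% | 20.6 / 19.8 | 17.3 / 16.6 | 0.96 | 1.17 |
| 25% / 35% | 20.9 / 19.5 | 17.5 / 16.4 | 0.94 | 1.14 |
| 20% / 40% | 21.5 / 18.8 | 18.0 / 15.8 | 0.88 | 1.07 |

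The first row also shows that with equal dropout the absolute 24-month risk is understated in both arms (20% appears as 16.9%), while the comparison is unaffected.

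**Allowing for follow-up after the last dose.** Extending each subject's counting window by 12 weeks (simulated under the same model, 20% event) moves the equal-hazard ratio from 0.94 to about 0.95 at 25% / 35%, and from 0.88 to about 0.90 at 20% / 40%.

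**Would rates alone be safe?** Take an event that occurs only in the first 3 months, with 10% risk and an identical hazard in both arms, and mean exposure of 22 months on placebo and 18 on active. Under exponential dropout that exposure implies about 16% and 45% dropout. The crude ratio is 0.97, close to correct. The ratio of events per subject-time is 1.19, a false excess on active, because the shorter arm loses denominator in months when no event can occur.

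**The case against.** The strongest case against has several parts.

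- Exposure-adjusted tables are commonly left to the statistical analysis plan, which is not at hand, so their absence is no error in itself. That is right as far as it goes. But the protocol defers other choices explicitly, such as the per-protocol criteria and the order of the secondary tests, and does not defer this one. It states a measure, and the point concerns that measure. If the analysis plan already adds rates, the point is met.
- A reader might infer that the active arm will look safer than it is. The documents do not support that. They give one overall dropout figure, and equal dropout gives a ratio of 1.00.
- A reader might also take a large gap, such as 22 against 18 months, as the expected case and conclude that a real excess would vanish. That gap needs about 16% against 45% dropout, which nothing in the documents suggests. At 25% / 35% a hazard ratio of 1.25 still shows as 1.14.
- The event that triggers the stop is itself counted, and each subject counts once per term. Only later, different events can be lost. This stands.
- The treatment-emergent definition has no end date, events are collected through Visit 15, and early stoppers are asked back at 12 and 24 months. This stands in part: some time at risk is recovered, but 12 weeks of extra counting changes the ratios little, and the later visits are sparse.
- The tables are descriptive, no between-arm test of adverse events is planned, and exposure by arm will be reported. An imbalance would be visible, but seeing it does not correct any particular event.

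**Conclusion.** The point holds in conditional form. The protocol's sole measure for adverse events is a crude percentage, and it has no safeguard if exposure differs by arm, which section 9.3.3 makes plausible. Over dropout splits from 27% / 33% to 20% / 40%, equal hazards would show a risk ratio of 0.96 to 0.88, and a true risk ratio of 1.22 would show as 1.17 to 1.07. These figures rest on assumed splits, a constant hazard and dropout independent of the event. With equal dropout the relative bias is nil.

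A further tempting reading is that rates should replace percentages for between-arm conclusions. The early-event example rules that out: for events concentrated in the first months the rate can mislead more than the percentage. Section 7.1 reports lymphocyte effects by Day 8 to 15, so such events are to be expected here.

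This is a worthwhile improvement to make before database lock. It does not invalidate the safety analysis, and no stopping rule is judged here.

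**What to change.** In section 9.7.1.8.2, keep the percentages and add beside them:

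1. Exposure-adjusted incidence rates for treatment-emergent events by SOC and PT, for serious events, and for the events of interest (infection, herpes, rash, lymphocytopenia, abnormal dreams): subjects with a first event per 100 subject-years at risk, with the between-arm difference and its 95% CI.
2. A stated end to the treatment-emergent window. At present only its start is defined, and the end sets both which events count and the denominator of the rate.
3. Cumulative incidence by arm for events concentrated early, such as rash and lymphocytopenia, where a constant hazard does not hold.

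The cost is one more set of tables from data already collected. The limitation to state with them is that the rates need a roughly constant hazard, so they should be read together with the percentages.

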9.7.1.8.3 LABORATORY VALUES

Laboratory results will be summarized using International System of Units, as appropriate. For all quantitative parameters listed in [Section 9.5.1.5.3](#), the actual value and the change from baseline to each postbaseline visit and to the end of treatment (defined as the last on-treatment value) will be summarized by visit and treatment group using descriptive statistics. Qualitative parameters listed in [Section 9.5.1.5.3](#) will be summarized using frequencies (number and percentage of subjects), and changes from baseline to each postbaseline visit and to end of treatment will be reported using shift tables. Percentages will be based on the number of subjects with both nonmissing baseline and relevant postbaseline results.

Laboratory test results will be assigned a low/normal/high (LNH) classification according to whether the value was below (L), within (N), or above (H) the laboratory parameter's reference range. Within-treatment comparisons for each laboratory parameter will be based on 3-by-3 tables (shift tables) that compare the baseline LNH classification to the LNH classification at each postbaseline visit and at the end of treatment. Similar shift tables will

also compare the baseline LNH classification to the LNH classification for the highest and lowest value during the treatment period.

[Appendix 1](#) (Sponsor's Grading for Laboratory Values) presents the criteria that will be used to identify subjects with treatment-emergent markedly abnormal laboratory values (TEMAVs). Except for phosphate, a TEMAV is defined as a postbaseline value with an increase from baseline to a Grade of 2 or higher. For phosphate, a TEMAV was defined as a postbaseline value with an increase from baseline to a Grade of 3 or higher. When displaying the incidence of TEMAVs, each subject may be counted once in the laboratory parameter high and in the laboratory parameter low categories, as applicable.

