9.7.1.8.4 VITAL SIGNS

Descriptive statistics for vital signs parameters (ie, systolic and diastolic BP, pulse, respiratory rate, temperature, weight), and changes from baseline will be presented by visit and treatment group.

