9.5.1.5.3 LABORATORY MEASUREMENTS

Clinical laboratory tests to be performed, including hematology, chemistry, urinalysis, and CSF are summarized in [Table 2](#). Subjects should be in a seated or supine position during blood collection. [Table 3](#) and [Table 4](#) show the visits and time points at which blood for clinical laboratory tests and urine for urinalysis will be collected in the study.

Table 2 Clinical Laboratory Tests

Category	Parameters
Hematology	Hematocrit, hemoglobin, platelets, red blood cell count, and white blood cell count with differential (bands, basophils, eosinophils, lymphocytes ^a , monocytes, neutrophils), prothrombin time, INR (derived from prothrombin time), and aPTT are to be performed for all subjects as part of Screening and at each visit (revised per Amendments 02 and 03). A prothrombin time and INR should also be performed prior to LP for subjects who consent to provide a CSF sample later in the study (ie, postrandomization) and are on anticoagulation/antiplatelet therapy (revised per Amendment 02)
Chemistry	
Electrolytes	Bicarbonate, calcium, chloride, phosphate, potassium, sodium
Liver function tests	Alanine aminotransferase, alkaline phosphatase, aspartate aminotransferase, gamma glutamyl transpeptidase, direct bilirubin, total bilirubin
Renal function tests	Blood urea/blood urea nitrogen, creatinine
Other	Albumin, cholesterol, globulin, glucose, lactate dehydrogenase, total protein, triglycerides, uric acid
Urinalysis	Bacteria, casts, crystals, epithelial cells, glucose, ketones, occult blood, pH, protein, red blood cells, specific gravity, white blood cells Urinalysis (sent to a central lab at Screening; assessed via dipstick at site during randomization phase)
Other	Viral screen (HCVAb [Hepatitis C] and HBsAg [Hepatitis B]). Viral characterization (HSV-1, HSV-2, and CMV) Serum pregnancy test (at Screening, females of child-bearing potential only) Urine pregnancy test (assessed via a dipstick at site during randomization phase, females of child-bearing potential only) Tests for thyroid function and vitamin B12 Blood samples for immunologic assessments. Some of the immunologic assessment blood sample will be used to prepare isolated PBMCs, which will be stored for testing if required. (revised per Amendments 01 and 03) Cerebrospinal fluid sampling (see Hematology [above] for INR testing)

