- ^d Unscheduled visits may be conducted at any time that additional assessments, including MRI scans, are clinically indicated in the judgment of the investigator. Note that not all assessments indicated under UNS Visits need be conducted – actual assessments needed will be determined by the investigator and will be based on the specific visit needs.
- ^e Only if clinically significant abnormalities are found at Visit 14 and the investigator considers it necessary to repeat at Visit 15.
- ^f Measurements of body temperature and sitting blood pressure and sitting heart rate will be obtained.
- ^g A full neurologic examination (including general status, cranial nerve function, motor system, coordination/cerebellar function, reflexes, and, sensory system) will be performed at Visit 13 (or ED). (revised per Amendment 01) Neurologic examinations at the other visits will focus on new symptoms and signs which will then alert the investigator to consider the occurrence of new CNS pathology. Examples of neurologic symptoms and signs that may indicate new CNS pathology that may need further investigation include (but are not limited to) visual disturbance, dysarthria, dysphasia, muscle strength, limb weakness, hyperflexia, paraparesis, micturition difficulty or urgency or incontinence, ataxia, neuropsychiatric or cognitive decline in excess of expectations based on the subject's recent history.
- ^h Please refer to the Concomitant Drug/Therapy [Section 9.4.7](#), which details prohibited and permitted medications in the study and associated time frames.
- ⁱ Single 12-lead standard ECGs will be recorded. If the QTcF is greater than 450 ms, perform 2 more 12-lead standard ECGs 1 minute apart and take the mean of the 3 QTcF values.
- ^j If dipstick urinalysis performed at site is abnormal, a urine sample will be sent to the central laboratory for full urinalysis.
- ^k More frequent testing may be required per local regulations. (revised per Amendment 04) If urine dipstick pregnancy test is positive, a blood sample will be drawn for serum pregnancy testing by the central laboratory.
- ^l Viral characterization will include testing for previous exposure to CMV, HSV1, HSV2, etc.

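### Post-Screening urine microscopy, and most conditional Visit 15 safety measures, exist only in subjects selected for an abnormal result, yet the planned by-visit tables treat them as routine data

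*Protocol*

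**What the plan says.** **Collection.** Section 9.5.1.5.3 (Table 2) lists the urinalysis parameters as "Bacteria, casts, crystals, epithelial cells, glucose, ketones, occult blood, pH, protein, red blood cells, specific gravity, white blood cells" and gives the method by phase: "Urinalysis (sent to a central lab at Screening; assessed via dipstick at site during randomization phase". Table 3 schedules the central test for every subject at Screening. Table 4 schedules a dipstick for everyone at each visit from Visit 2 to Visit 14, with footnote j: "If dipstick urinalysis performed at site is abnormal, a urine sample will be sent to the central laboratory for full urinalysis". At Visit 15 the physical examination, vital signs, ECG and dipstick carry footnote e: "Only if clinically significant abnormalities are found at Visit 14 and the investigator considers it necessary to repeat at Visit 15". Weight, chemistry and hematology at Visit 15 carry no such condition.

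**Analysis.** For the qualitative parameters of Section 9.5.1.5.3, Section 9.7.1.8.3 prescribes frequencies and adds that "changes from baseline to each postbaseline visit and to end of treatment will be reported using shift tables". The denominator rule follows: "Percentages will be based on the number of subjects with both nonmissing baseline and relevant postbaseline results". It makes no exception for tests done only on a trigger. Section 9.7.1.8.4 says of vital signs, among which it counts weight, that descriptive statistics "and changes from baseline will be presented by visit and treatment group". Section 9.7.1.8 summarizes ECG findings by treatment group and states neither a by-visit table nor a denominator.

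The protocol file holds text from more than one version. The Version 5.0 schedule and the Version 5.0 analysis section belong together, and the later version's laboratory text is identical, so the conflict lies within one version.

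**The concern.** A both-results-present denominator is harmless when results are missing for reasons unrelated to the measurement. Here the postbaseline microscopy result is present because a concurrent test of the same urine was abnormal. The baseline result carries no such condition.

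Two things are at stake. Within an arm, the abnormal share at each visit is inflated and can look like treatment-emergent change. Between arms, the comparison is conditional on a post-randomization event, the abnormal dipstick, so it is no longer a comparison in the Safety Analysis Set. If the drug raised the number of abnormal dipsticks, the extra cases would enter numerator and denominator together and the signal could vanish from the percentages.

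Visit 15 raises a related question: a by-visit row for measures repeated only after an abnormal Visit 14 does not describe the study population.

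**Working it through.** The protocol states no figure on this point, so there is none to reproduce. All rates below are assumptions, chosen to show the range, and there is no drug effect unless stated.

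**1. Microscopy share in the table.** Let p be the true abnormal rate, constant over time, and let Se and Sp be dipstick sensitivity and specificity for it.

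- Share tested = p·Se + (1−p)(1−Sp)
- Share abnormal among tested = p·Se / [p·Se + (1−p)(1−Sp)]

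| p | Se | Sp | Tested | Abnormal among tested |
|---|---|---|---|---|
| 5% | 50% | 95% | 0.025 + 0.0475 = 7.25% | 34% |
| 5% | 50% | 90% | 0.025 + 0.095 = 12% | 21% |
| 5% | 90% | 95% | 0.045 + 0.0475 = 9.25% | 49% |
| 5% | 90% | 90% | 0.045 + 0.095 = 14% | 32% |

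With 665 per arm (Section 9.7.2) and no dropout, 7.25–14% is about 48–93 subjects. The abnormal share among tested is 13–36% at p = 3% and 36–67% at p = 10%.

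**2. Apparent shift.** The rule requires both results, so the baseline margin also comes from the triggered subjects.

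- No within-subject persistence: their baseline rate is 5%, and the table reads 5% to 21–49%.
- Full persistence: their baseline rate equals their postbaseline rate, and no shift appears.

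The truth lies between these limits.

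**3. Second parametrization.** Assume a dipstick-abnormal rate of 5–30%, microscopy abnormal in 30–90% after an abnormal dipstick and in 2–10% after a normal one. The table shows 30–90%; the all-subject rate is 3.4–34%. The ratio runs from 1.9 to 14.1, on 33–200 of 665 subjects. Example: 10%, 60% and 2% give 0.10×0.60 + 0.90×0.02 = 7.8% in all subjects against 60% shown (ratio 7.7; about 66 subjects).

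**4. Masking a drug effect.** Suppose placebo has 66 of 665 triggered and 40 abnormal, and drug has 132 of 665 triggered and 80 abnormal. The table shows 40/66 = 61% and 80/132 = 61%. Over all subjects the rates are 40/665 = 6% and 80/665 = 12%.

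**5. Visit 15.** Systolic pressure was simulated (1,000,000 draws; mean 135, SD 15), with selection if Visit 14 was ≥160 or ≤105. Investigator judgement was not modelled. About 7% of subjects are selected, and 17–47% of them are out of range at Visit 15, against 7% of all subjects.

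- Baseline correlated with Visit 14 as strongly as Visit 15 is (0.4, 0.6 or 0.8): mean change from baseline is about 0, and the same subjects were out of range equally often at baseline (17%/17%, 29%/28%, 47%/47%).
- Correlation weaker with the distant baseline (0.7 near and 0.4 far, or 0.8 and 0.5): mean change is +9.3 when only high values select and +2.9 when both tails do.

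**The case against.** A reader might infer that microscopy, Visit 15 vital signs and ECG all show worsening by construction. The documents do not support that.

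- The both-nonmissing rule restricts the baseline margin too, so setting an all-subject 5% beside 21–49% gives only the no-persistence limit.
- The rule is written for laboratory percentages. Section 9.7.1.8.4 states no denominator for vital signs, and Section 9.7.1.8 states no by-visit ECG table.
- At Visit 15 the trigger needs a clinically significant finding and investigator judgement, and change from baseline can be nil.
- Analytes the dipstick reads are recorded in everyone through Visit 14, so they are not selectively missing before Visit 15.

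All four stand, and they limit the point.

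Three further arguments carry less weight. First, the trigger is the same in both blinded arms. That removes a spurious arm difference when the drug does nothing; it does not protect the comparison when the drug affects the dipstick. Second, choosing the baseline record and handling reflex tests is ordinary analysis-plan work, and Section 9.1.2.1 already places a dipstick among the Visit 2 baseline procedures. But the protocol has not left the denominator open: it fixes a rule without exception. Third, the damage is contained. Appendix 1 has no urinalysis parameter, so the markedly abnormal value analysis is untouched. The end-of-treatment and highest/lowest tables use on-treatment or treatment-period values, so Visit 15 does not enter them.

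**Conclusion.** The point holds for urine microscopy. As written, the rule computes percentages in a dipstick-positive subset, overstates the abnormal share, tends towards spurious normal-to-abnormal shifts, and can hide a real arm difference. Under the stated assumptions at 5% prevalence, 21–49% would read as abnormal in 7–14% of subjects. The apparent shift ranges from none up to about 5% to 21–49%, depending on persistence, which the documents do not give. The direction of the overstatement requires only that microscopy is abnormal more often after an abnormal dipstick than after a normal one.

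For Visit 15, selection is certain for dipstick, vital signs other than weight, and ECG. A Visit 15 row in the by-visit vital-signs or dipstick tables would describe a selected few. Worsening there is possible but not automatic, and for ECG the protocol states no by-visit table to correct.

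This concerns safety displays only and leaves the efficacy analysis alone. It should be put right before the table shells are final.

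**What to change.** In Section 9.7.1.8.3, and in the table shells:

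1. For analytes the dipstick reads, take the Visit 2 dipstick as baseline and compare dipstick with dipstick.
2. For microscopy-only items, drop the shift table. At each visit report the number with a central-laboratory abnormality over all subjects who had a dipstick at that visit.
3. List the conditional Visit 15 vital signs, ECG and dipstick results instead of tabulating them. Keep Visit 15 weight in the by-visit summary, because it is collected unconditionally.

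The cost is wording and shells; no visit, procedure or clinical rule changes. The downside is that a microscopy abnormality behind a negative dipstick counts as not abnormal. With p = 5% and sensitivity 50–90%, the reported rate would be 0.05×0.50 = 2.5% to 0.05×0.90 = 4.5%. That understatement should be footnoted. It is smaller than the present overstatement, and the denominator no longer depends on the dipstick result.
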